1.2 Primary Study Endpoints

State the primary endpoints to be measured in the study. Clinical trials typically have a primary objective or endpoint. Additional objectives and endpoints are secondary. The endpoints (or outcomes), determined for each study subject, are the quantitative measurements required by the objectives. Measuring the selected endpoints is the goal of a trial (examples: response rate and survival).

This study will measure changes in participants' policy knowledge and skills, policy engagement, and the extent to which research activities are informed by public officials' needs.

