All data will be handled in accordance with the consent procedures and IRB protocol. Identifiers will be stripped from the data files for archival storage. Identifying information will be destroyed within three years of the end of the project. De-identified study data will be archived indefinitely. Identifying info will be destroyed within three years of the end of the project.

Analyses for survey outcomes for researchers and legislative staff follow similar patterns and will be conducted in *MPlus* or *SAS*. For researchers, logistic models will be used to model researchers' change from baseline in 1) knowledge of current lobbying restrictions, 2) belief that engaging with policymakers would improve their own research, and 3) level of policy engagement. For legislative staff, generalized linear models will be used to model the trial groups on how much congressional offices value URE for 1) conceptual, 2) instrumental, and 3) tactical purposes

For legislative offices, we will assess the impact of the RPC on both proposed and enacted bills. Since the continuity of relevant legislative activity may be inconsistent between short intervals due to Congressional recesses (e.g., 3-month survey timeframes), legislative activity will be analyzed and compared between two time periods: one-year before RPC implementation (baseline) and six months following RPC implementation (post-assessment). The indicators for evidence use in this

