project will reflect having used research evidence language in legislation related to the wellbeing of children and families, as determined by trained coders, on which the office is listed as a sponsor or original cosponsor. This outcome is dichotomous: did or did not sponsor or originally cosponsor legislation that was coded as having used research evidence. Therefore, logistic regression analyses will assess use of research evidence. Given the cyclical nature of Congress, it is expected that overall legislative productivity will be different at baseline than at the post-assessment. Thus, the control and intervention groups will be compared to one another at each timepoint separately. They will be compared at baseline to establish if there is a difference in sample, perhaps due to self-selection biases. If there is no difference at baseline, we will compare the use of research evidence in legislation among control offices and intervention offices at the post-assessment time period. We will regress dichotomous post-assessment use of research evidence on group assignment. Similar logistic regressions will be conducted on the probability of an office writing 1) a bill related to the wellbeing of children and families and 2) a bill that did not include URE research evidence terms.

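### Three equally ranked primary domains, modelled as three separate researcher outcomes, have no stated alpha, order or multiplicity control; the six staff and legislative outcomes have no stated rank

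*SAP*

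**What the plan says.** Protocol section 1.2 (Primary Study Endpoints) says that the study will measure "changes in participants' policy knowledge and skills, policy engagement, and the extent to which research activities are informed by public officials' needs". The three domains stand side by side, and none is called the main one. Section 1.3 lists as secondary only the collaboration experiences of the intervention group.

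The SAP's Data Analysis Plan sets out three blocks of analyses:

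- **Researchers:** "logistic models will be used to model researchers' change from baseline in 1) knowledge of current lobbying restrictions", followed by "2) belief that engaging with policymakers would improve their own research, and 3) level of policy engagement".
- **Legislative staff:** generalized linear models comparing the trial groups on "how much congressional offices value URE for 1) conceptual, 2) instrumental, and 3) tactical purposes".
- **Legislative offices:** "We will regress dichotomous post-assessment use of research evidence on group assignment", and then "Similar logistic regressions will be conducted on the probability of an office writing 1) a bill related to the wellbeing of children and families" and, second, a bill without research evidence terms.

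That makes nine outcomes. The SAP calls none of them primary or secondary. Neither document states an alpha, sidedness, a testing order, a family of tests or an adjustment. The main legislative comparison goes ahead only if the groups do not differ at baseline. That is a condition for running the analysis and does not control type I error across outcomes.

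**The concern.** With three primary domains of equal standing and a separate test for each researcher outcome, the plan leaves open what result would support a conclusion that the RPC affects researchers. If one nominally significant outcome out of three is enough, the error rate of that conclusion exceeds the level of each test.

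The six remaining outcomes raise a different difficulty. Protocol 1.1 gives the overall aim as the effect of the RPC on research use in federal policymaking, which the legislative outcomes address most directly. Yet Protocol 1.2 makes researcher outcomes primary, and section 7.2.2 gives the public-record data a role in interpreting the key findings. The SAP then presents all nine without rank. A reader of the final report could not tell from the plan whether a significant staff or legislative result was confirmatory, supportive or a chance finding.

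**Working it through.** **Inputs**

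- Researcher outcomes: 3 (SAP, Data Analysis Plan). Primary domains: 3 (Protocol 1.2).
- Staff outcomes: 3. Legislative outcomes: 3 (SAP).
- Alpha per test: not stated. I assume two-sided 0.05 and show 0.01 and 0.10.
- Correlation between outcomes: not stated. I show 0 to 0.9.
- One test per researcher outcome is also an assumption, because the SAP does not name the follow-up survey at which change is judged.

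The documents give no familywise error figure to reproduce.

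**Step 1: independent tests, all three nulls true.** The formula is 1 − (1 − α)^m.

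- α = 0.05, m = 3: 1 − 0.95^3 = 14.3%
- α = 0.01, m = 3: 1 − 0.99^3 = 3.0%
- α = 0.10, m = 3: 1 − 0.90^3 = 27.1%

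**Step 2: correlated tests.** These figures come from simulating three two-sided z-tests with a common correlation at α = 0.05 (1,000,000 draws).

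| Correlation | At least one false positive in three |
|---|---|
| 0 | 14.3% |
| 0.3 | 13.7% |
| 0.5 | 12.6% |
| 0.7 | 10.9% |
| 0.9 | 8.4% |

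A second simulation (400,000 draws) gave 12.5% at correlation 0.5. Correlation reduces the excess, but the error stays above 5% at every value examined.

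**Step 3: effect of the remedy.** Holm compares the smallest p-value with 0.05/3 = 0.0167, the next with 0.05/2 = 0.025 and the largest with 0.05. With all three nulls true, an error needs the smallest p-value to fall below 0.0167. If the tests are independent, that probability is 1 − (1 − 0.0167)^3 = 4.9%. Holm keeps the familywise error at or below 5% under any correlation.

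**Step 4: cost in power.** By normal approximation, a test with 80% power at 0.05 has a standardised effect of 1.960 + 0.842 = 2.802. The critical value at 0.0167 is 2.394, so power is Φ(2.802 − 2.394) = 65.8%. For 90% power, Φ(1.960 + 1.282 − 2.394) = 80.2%. The later Holm steps are less strict, so these are the largest losses from those starting points.

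**Step 5: the same cost at this trial's target.** The 90% power that the SAP claims for an effect of 0.2 does not reproduce at 40 per arm. Reading 0.2 as a standardised mean difference, the standardised effect is 0.2 × √(40/2) = 0.894. Power is then Φ(0.894 − 1.960) = 14.3% at 0.05, and Φ(0.894 − 2.394) = 6.7% at 0.0167. The low starting power is a separate issue, but it shows that Step 4 describes generic starting points.

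**Step 6: matching outcomes to domains.** Level of policy engagement fits the engagement domain. Knowledge of lobbying restrictions covers part of the knowledge-and-skills domain, and none of the three models covers skills. A belief that engagement would improve one's own research is not the same as research activities being informed by officials' needs.

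**The case against.** The strongest reply is that the plan is silent and does not adopt a faulty rule. Nothing in it says that one significant outcome out of several proves the RPC effective. If the intended claim required all three researcher outcomes to succeed, no adjustment would be needed; if each outcome carried its own separate claim, many would accept unadjusted tests. This is fair, and it limits the point: the inflation is conditional on how the results are used. But neither document states either rule, and equal primary rank without a rule leaves the any-one-of-three reading open.

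A reader might go further and infer that the study's false-positive rate is 37%, from 1 − 0.95^9 = 37.0%. The documents do not support that. The figure needs nine independent tests, every null true, and one family spanning researchers, staff and offices, which no section defines. The evidence-use outcome is restricted to child and family legislation, so it overlaps by definition with the outcome of writing such a bill. A bill without evidence terms is not a measure of evidence use. At a common correlation of 0.5 the nine-test figure is about 27%. At most, 37% is the independence upper figure for nine tests treated as one family. Nor is nine a firm count: the SAP mentions both proposed and enacted bills and does not say whether they are analysed separately.

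A reader might also take the three SAP researcher outcomes to be the three protocol primary endpoints. They match only loosely, as Step 6 shows. Naming them the primary family without settling the match would fix that mismatch in place.

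**Conclusion.** The point holds for the three researcher outcomes. At an assumed two-sided 5% per test, the chance of at least one false positive is about 8% to 14% for correlations from 0.9 down to 0, or roughly 1.7 to 2.9 times the nominal level. It rests on three assumptions: all three nulls are true, there is one test per outcome, and any single success would be reported as a primary finding.

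For the six staff and legislative outcomes the defect is undefined status, and no error rate should be attached to them. This is worth correcting before analysis because it changes what a single significant result can support. It does not bias the effect estimates.

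**What to change.** In the SAP:

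1. State the significance level and sidedness, for example a two-sided 5% overall.
2. State which researcher outcome represents each primary domain in Protocol 1.2, and resolve the gaps for skills and for research informed by officials' needs. Name the follow-up time point for each test.
3. Test those three outcomes with the Holm procedure at the stated overall level.
4. Label the staff and legislative outcomes secondary or exploratory. Report them as estimates with confidence intervals, and say that none of them alone is proof that the RPC works. State whether proposed and enacted bills are analysed separately.

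The change is to wording only and needs no new data. It costs the power shown in Step 4. Power at the 40-per-arm target is probably well below the stated 90% even before adjustment; that needs its own correction and is no reason to leave the primary family undefined.

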8.3 Statistical methods

Describe the statistical methods (or non-statistical methods of analysis) that will be employed.

Surveys data will be analysed longitudinally by modelling change across 4 time points—including repeated measures and multilevel growth curve models (MLM) using *MPlus*. Missing data will be handled with multiple imputation.

Qualitative interview data will be analyzed using a thematic process followed by an intensive discourse analysis. Data will be interpreted alongside observational data using an interpretive policy analysis to develop a data-driven theoretical framework for describing evidence use in the RPC.

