Evaluation of the Research to Policy Collaboration Model

NCT03671434

September 16, 2021

Statistical Analysis Plan

Sample Size Justification

Statistical analyses are all powered at least at a 90% level to detect effect sizes of 0.2 or greater (power analysis conducted with *Optimal Design plus Empirical Evidence*).

We aim to enroll a maximum of 300 researchers in the baseline period of this study. The target number of study participants in the full study is 80, including 40 researchers in the intervention and 40 researchers in the control group. This level of oversampling is required because not all researchers will complete all phases of the intervention and oversampling will combat attrition from study participation.

It is anticipated that around 300 researchers will be recruited for the RPC. We believe that at least $\frac{3}{4}$ ($n = 225$) of those may participate in the study at baseline, and approximately half of those individuals may complete the study ($n = 112$), which would over-sample for the current study.

Data Quality Plan

Participants will fill out the surveys directly, minimizing possible errors associated with manually entering data. The surveys will be deployed through *REDCap*, which has integrated data quality procedures, such as an approval routing process for any changes to an active survey to ensure it will not remove or alter existing data. The legislative coding will be completed by trained coders who meet an acceptable level of reliability ($\alpha = .70$). Thirty percent of the sampled legislation will be double-coded to ensure high-quality and reliable data.

Missing data will be handled with multiple imputation because this is best practice when data are not missing at random. This method will be guided by Lee and colleagues' approach to multiple imputation for multilevel data, which reduces and checks for biases in imputed estimates (e.g., tests for convergence and model fit) and suggests that there must be at least 50% complete data and incorporating auxiliary variables highly correlated with the imputed variable (e.g., outcome variables assessed at prior time points).

Data Analysis Plan

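### The staff survey models make no provision for several respondents from one office, although the legislative groups are described by office

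*SAP*

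**What the plan says.** The Data Analysis Plan of the SAP treats survey outcomes and legislation outcomes separately. On the surveys it says "Analyses for survey outcomes for researchers and legislative staff follow similar patterns", and the researchers are analysed as individuals. For staff it then says "For legislative staff, generalized linear models will be used to model the trial groups on how much congressional offices value URE", for three purposes: conceptual, instrumental and tactical. The sentence lists no model terms and no variance estimator, and it does not say whether a record is a staff member or an office.

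The legislation paragraphs that follow use the office as the unit. The plan there is "we will compare the use of research evidence in legislation among control offices and intervention offices at the post-assessment time period", and "We will regress dichotomous post-assessment use of research evidence on group assignment".

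Multilevel methods are named in two other places. The SAP's Data Quality Plan follows a published "approach to multiple imputation for multilevel data", which concerns missing data. Protocol Section 8.3 plans multilevel growth curves for survey change over four time points, and the Protocol describes surveys of researchers only. Neither place deals with staff nested in offices.

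**The concern.** If groups are formed by office, all staff of one office share a trial group. They also share an employer and its working habits, and they are asked about something the SAP words as a property of the office ("how much congressional offices value URE"). Positive correlation between colleagues' answers is therefore the natural expectation. A generalized linear model that treats such answers as independent counts more information than there is.

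Confidence intervals for the RPC effect on the three staff outcomes would then be too narrow, and false positive findings more frequent than the nominal level. If the SAP stays silent, the choice between an independent and a clustered analysis can also be made after the data are seen.

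**Working it through.** **The plan's own figure.** The only related figure is the SAP's statement "Statistical analyses are all powered at least at a 90% level to detect effect sizes of 0.2 or greater". The SAP gives sample sizes for researchers (target 40 per group) and none for staff or offices, so the statement cannot be reproduced for the staff analysis. For the researchers, take an effect of 0.2 SD and two-sided alpha 0.05 (neither the metric nor alpha is stated). A simple comparison of 40 per group then has about 14% power, and 90% would need 2 × (1.960 + 1.282)² / 0.2² ≈ 526 per group. That is a separate matter and does not decide this point.

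**Inputs for the clustering check**
- Model: a generalized linear model on trial group, with no provision for office (SAP, Data Analysis Plan).
- Grouping by office: from the legislation paragraphs of the same plan.
- Respondents per office, m: not in the documents. Assumed 2 to 3, with 1 as the reference case.
- Intra-office correlation, ICC: not in the documents. Assumed 0.1 to 0.3, with 0 as the reference case.
- Nominal two-sided level: 5%, assumed.

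**Formulas** (equal m in all offices, large-sample approximation)
- Design effect: DE = 1 + (m − 1) × ICC
- True SE / naive SE = √DE
- Actual type I error = 2 × [1 − Φ(1.96 / √DE)]

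**Two cases worked through**
- m = 2, ICC = 0.1: DE = 1 + 1 × 0.1 = 1.1; √1.1 = 1.049; 1.96 / 1.049 = 1.869; type I error 6.2%.
- m = 3, ICC = 0.3: DE = 1 + 2 × 0.3 = 1.6; √1.6 = 1.265; 1.96 / 1.265 = 1.549; type I error 12.1%.

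| m | ICC | DE | True SE / naive SE | Actual type I error |
|---|---|---|---|---|
| 1 | any | 1.0 | 1.00 | 5.0% |
| any | 0 | 1.0 | 1.00 | 5.0% |
| 2 | 0.1 | 1.1 | 1.05 | 6.2% |
| 2 | 0.3 | 1.3 | 1.14 | 8.6% |
| 3 | 0.1 | 1.2 | 1.10 | 7.4% |
| 3 | 0.3 | 1.6 | 1.26 | 12.1% |

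The same numbers give the coverage of a nominal 95% interval: from 100 − 6.2 = 93.8% down to 100 − 12.1 = 87.9%.

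**Sensitivity.** Over a wider range, m = 2 to 4 and ICC = 0.05 to 0.5, the ratio runs from 1.02 to 1.58 and the type I error from 5.6% to 21.5%. The result depends heavily on two quantities that the plan does not give.

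**The case against.** A reader might infer that the SAP commits to one row per staff member with independent errors, and that its standard errors are therefore wrong. The documents do not support that.

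- **The unit is open.** The outcome is worded at office level, which also fits a single informant or a single value per office. In either case there is no defect.
- **Silence is not a choice.** The staff sentence lists no terms at all. The absence of an office effect is under-specification, not a stated preference for independent errors.
- **Two conditions are needed.** There must be more than one respondent per office and a positive correlation. The documents establish neither, and at zero correlation several respondents do no harm.
- **Office grouping is carried over.** It is stated for legislation; the staff sentence refers only to trial groups. Neither document describes how offices or staff were assigned, and the SAP itself raises possible self-selection.
- **The remedy depends on the number of offices.** Uncorrected cluster-robust errors are themselves too small when clusters are few.

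All of this stands as a limit on the claim, but it does not close the gap. The SAP separates staff from offices and likens the staff analyses to those of individually analysed researchers, so the per-respondent reading is the more natural one. The only grouping described on the legislative side is by office. Nothing caps respondents at one per office, and no step combines answers within an office. The multilevel wording elsewhere does not help, because it covers imputation and growth over time. The model as named is correct only if m = 1 or ICC = 0, and the plan guarantees neither.

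**Conclusion.** The point holds in conditional form. The staff analysis has no stated unit and no provision for within-office correlation, while the legislative groups are described by office. Under the assumed 2 to 3 respondents per office and ICC of 0.1 to 0.3, the naive standard error should be multiplied by about 1.05 to 1.26, and a nominal 5% test has an actual level of about 6% to 12%. That is modest at one end and material at the other, and it would apply to each of the three staff outcomes. It rests on those two assumptions and on group membership being by office. It says nothing about the researcher outcomes or the office-level legislation analyses. The change should be made, because it keeps the analysis valid whatever number of staff respond.

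**What to change.** In the staff part of the SAP's Data Analysis Plan:

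1. State that office is the unit of assignment, as the legislation paragraphs already imply, and say how many staff per office may respond and how many offices are expected.
2. State that, where an office has more than one respondent, the staff models will use GEE or cluster-robust standard errors by office, with a small-sample correction if offices are few. Alternatively, average responses to one value per office and compare office means.
3. Do not make a random office intercept the general rule. With one respondent per office and a Gaussian outcome it cannot be separated from residual error.

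The cost is a few lines of text and a standard option in the software. Intervals will be somewhat wider if clustering is present, which is the correct result, and a correction is needed if offices are few. With one respondent per office the results are essentially unchanged.

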7.2.2 EXAMPLE: Visit 2 or Day 2 or Post-test, etc. (format accordingly)

Provide a description as defined above and format accordingly.

The same survey protocol as used in the pre-test will be administered approximately every three months for about one year: (2) Subsequent to training, (3) Subsequent to policy engagement, and (4) Follow-up. Efforts to minimize survey attrition will include tracking non-responses to follow-up surveys and requesting survey participation via individual emails twice per week until survey completion or until the 3-week window for survey participation ends or until the participant opts-out of participating in the survey. In the last week of the survey window, survey participants who have not yet participated or opted-out of participation will be contacted by phone to request their participation and to complete the survey over the phone if needed.

Qualitative interviews will occur subsequent to the RPC implementation, approximately 9 months following study enrollment, using web-chat or phone. These interviews will ask:

- How did you become involved in the RPC? Is this your first involvement with policy? With legislation? If no, what are your previous experiences?

- What were your expectations and aspirations from involvement in the RPC?
- Can you describe the interactions you've had with policymakers through the RPC? (e.g. informal coffees, phone calls, formal meetings, etc). How does this compare to interactions outside the RPC?
- What kinds of evidence have you seen and used as part of the RPC? How? Did this reflect your expectations?
- What has worked well? What could have gone better? (Risks of interaction, perceptions and stereotypes)

This study also involves non-human research data, drawing from public information regarding public officials' use of research evidence, which will be obtained from legislators' sponsored bills, public statements, and reported research use by public officials. Non-human research data will also support the interpretation of key findings from the current investigation that involve human subjects.

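### The legislative comparison is conditional on an undefined baseline check, has no plan if the check fails, and leaves the measured baseline out of the model

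*SAP*

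**What the plan says.** The SAP's Data Analysis Plan assesses the RPC's effect on legislation at office level. "This outcome is dichotomous: did or did not sponsor or originally cosponsor legislation that was coded as having used research evidence". Baseline is the year before RPC implementation; the post-assessment window is the six months after it.

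The SAP explains why it does not model change: "Given the cyclical nature of Congress, it is expected that overall legislative productivity will be different at baseline than at the post-assessment". It continues: "Thus, the control and intervention groups will be compared to one another at each timepoint separately". On the baseline comparison it says: "They will be compared at baseline to establish if there is a difference in sample, perhaps due to self-selection biases". The condition follows: "If there is no difference at baseline, we will compare the use of research evidence in legislation among control offices and intervention offices". The model is then given: "We will regress dichotomous post-assessment use of research evidence on group assignment". Similar logistic regressions are planned for two companion outcomes: any bill on child and family wellbeing, and a bill without research terms.

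The rest of the documents does not fill the gaps:

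- Protocol 8.3 covers only the researcher surveys and the interviews.
- Earlier values of an outcome appear in the SAP's Data Quality Plan, but only as auxiliary variables for imputation.
- Protocol 4.1 and 7.1 describe randomisation of researchers. Neither document says how offices were allocated.

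**The concern.** Three things are missing from a rule that decides whether an analysis takes place. No test, significance level or margin defines when the groups count as equal at baseline. Nothing says what happens if they do not. The model omits the baseline value of the same outcome, which is already collected for each office.

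Because allocation of offices is not stated, two cases have to be kept apart.

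- **Randomised offices.** Any baseline difference is chance. The check then guards against nothing and leaves some trials with no planned comparison. The group-only estimate is unbiased on average; the cost is lost power, plus bias conditional on whatever imbalance occurred.
- **Self-selected offices**, a possibility the SAP raises. A non-significant baseline test does not show comparability, and a group-only model carries part of any missed gap into the reported effect.

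In both cases, if a difference is found, the analyst must choose the analysis after seeing data. The stated reason about productivity does not argue against a baseline covariate. A shift between periods that is common to both arms goes into the intercept, and the covariate compares offices within the post-assessment period.

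**Working it through.** The documents contain no figure to reproduce for this analysis. The SAP's general power statement (90% for an effect size of 0.2) says nothing specific to offices.

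**Inputs, all assumed:** 50 or 100 offices per arm; two-sided 5% logistic Wald tests; baseline check at p<0.05 unless stated; correlation r between the normal variables underlying baseline and post status of 0.3, 0.5 or 0.7. There were 20,000 simulated trials per setting, or 40,000 for the threshold runs and the measured-baseline route.

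**Case 1: randomised.** Baseline is 50% in both arms; post rates are 35% and 55%. Hand check of the group-only test at 50 per arm:

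- SE = √[(0.35×0.65 + 0.55×0.45)/50] = 0.0975.
- z = 0.20/0.0975 = 2.05.
- Power ≈ Φ(2.05 − 1.96) ≈ 0.54.

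At 100 per arm, SE = 0.0689, z = 2.90 and power ≈ 0.83. The condition multiplies power by the chance of passing: 0.541 × (1 − 0.057) = 0.510.

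| Per arm | Comparison stopped by chance | Conditional, group only | Unconditional, group only | Unconditional, baseline-adjusted (r = 0.3 / 0.5 / 0.7) |
|---|---|---|---|---|
| 50 | 5.6–5.8% | 51.0–51.6% | 54.1–54.5% | 53.4 / 56.8 / 62.3% |
| 100 | 5.5–5.7% | 78.4–78.5% | 82.6–82.9% | 83.1 / 85.5 / 90.2% |

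A looser check stops more trials: 9–10% at p<0.10 and about 19% at p<0.20. With no effect (40% at both times), type I error is 4.1–5.0% conditional and 4.6–5.2% adjusted, with mean bias 0.

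**Case 2: self-selected, no RPC effect.** True baseline is 45% against 30%. Hand check of the baseline test's power:

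- 50 per arm: SE = √[(0.45×0.55 + 0.30×0.70)/50] = 0.0957; z = 0.15/0.0957 = 1.57; power ≈ Φ(−0.39) ≈ 0.35.
- 100 per arm: SE = 0.0676; z = 2.22; power ≈ Φ(0.26) ≈ 0.60.

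Simulation gives 34–35% and 58–60%, so the check misses this gap in about 65% and 41% of trials.

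If the gap acts only through the measured baseline, the expected group-only difference over all trials is carry-over slope × gap: 0.18×15 = 2.7, 0.32×15 = 4.8 and 0.48×15 = 7.2 points. Restricting to trials that pass the check shrinks this but does not remove it:

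| Route of the gap | Per arm | Mean group-only difference in passing trials, points (r = 0.3 / 0.5 / 0.7) | Adjusted, all trials, points |
|---|---|---|---|
| Measured baseline only | 50 | 1.8 / 3.1 / 4.7 | 0 |
| Measured baseline only | 100 | 1.6 / 2.7 / 4.1 | 0 |
| Underlying propensity | 50 | 3.3 / 5.6 / 7.7 | 1.5 / 2.5 / 3.1 |
| Underlying propensity | 100 | 3.1 / 5.2 / 7.3 | 1.5 / 2.5 / 3.1 |

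False positives among passing trials, over both routes, are 4.6–10.4% at 50 per arm and 5.4–16.2% at 100.

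**Is dropping the condition enough?** A separate simulation (3,000 trials per setting) used a true baseline of 40% against 60%, no effect, and a baseline-to-post odds ratio of 4 or 10, with the gap acting through the measured baseline. False-positive rates were:

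| Per arm | Unconditional, group only | Group only, passing trials | Unconditional, adjusted |
|---|---|---|---|
| 50 | 10.5–19.4% | 6.5–7.1% | 4.6–5.2% |
| 100 | 15.8–34.4% | 7.2–9.3% | 4.9–5.1% |

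Without randomisation, removing the condition but leaving the covariate out would make matters worse. The two changes belong together.

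**The case against.** **The text can be read more kindly.** The sentence on separate comparisons at each timepoint and the sentence giving the model carry no condition, so the conditional sentence might describe only the straightforward case. But it comes after the general statement and qualifies it. Even on the kinder reading, the plan does not say what is done after a baseline difference.

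**Self-selection is only a possibility.** The SAP offers it as one explanation of a difference, and its references to group assignment and trial groups lean towards allocation by the study. That is fair, and the documents do not settle it. Under randomisation there is no average bias, type I error stays near 5%, and removing the condition is worth about 3 to 5 points of power.

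**The covariate may add little.** At r = 0.3 and 50 per arm, the adjusted model has marginally less power than simply dropping the condition (53.4% against 54.1%). A low correlation is plausible because the windows are 12 and 6 months. This stands.

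**Counted per trial started, the condition limits false claims.** On the underlying-propensity route, the conditional procedure gives 3.9–6.9% false positives at 50 per arm and 2.8–6.7% at 100, because it often reports nothing. The adjusted model, always run, gives 5.3–6.4% and 5.5–8.1%. This also stands. It describes a rule that is protected mainly by having no result in 34–59% of trials. Among trials that do report, the adjusted model is better (5.3–8.1% against 5.8–16.4%).

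**The role is supporting.** The legislative outcome is not among the endpoints in Protocol 1.2 and 1.3, and Protocol 7.2.2 says "Non-human research data will also support the interpretation of key findings". That limits the severity.

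**Conclusion.** The concern holds. The comparison is conditional on an undefined check, has no alternative branch, and uses a model without the measured baseline. That rests on the text alone.

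The sizes are illustrative, because office numbers, event rates, correlations and the check's threshold are all assumed, and the power scenario uses one set of rates. If offices were randomised, the condition costs about 3 to 5 points of power; the covariate adds between about −1 and +8 points beyond that. If they self-selected with a 15-point baseline gap, passing trials report a spurious 2 to 8 points, and adjustment leaves 0 to about 3.

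This should be fixed, but it does not threaten the trial's stated endpoints. It matters because this is the SAP's planned test of the RPC's effect on legislation.

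**What to change.** In the legislative part of the Data Analysis Plan:

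1. Delete the condition on the baseline comparison, and describe baseline by group without a test that decides the analysis.
2. Always fit the logistic regression of the post-assessment outcome on assigned group, with the office's baseline value of the same outcome as a prespecified covariate. Report the adjusted risk difference with the odds ratio.
3. Use the same form for the two companion outcomes, each with its own baseline value.
4. State how offices were allocated. If they self-selected, say that one binary baseline covariate does not remove all confounding.

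The cost is three or four sentences and no new data. The model becomes slightly more complex, with little or no precision gain over an unconditional group-only test if the baseline–post correlation is about 0.3 or lower.
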